2.4.1 Initial Dose Escalation

Subjects who completed day 1 but not day 2 of initial dose escalation at the time remote procedures were implemented will stop study product dosing until regular study site visits resume. When study site visits resume, day 1 of initial dose escalation will be repeated following discussion and approval from the medical monitor ([Section 4.2](#)).

2.4.2 Up-Dosing Period

The duration of up-dosing for individual subjects will be extended to accommodate any delays due to the restrictions.

Subjects in the up-dosing period of study treatment will continue daily dosing with study product at their current dose level until the next study site visit. Dose adjustments may be allowed ([Section 4.1, Table 1](#)). No up-dosing will be allowed until the next study site visit.

When study site visits resume, study treatment will continue or resume under medical supervision at the study site as follows:

- Subjects who continued dosing at their current dose level or a lower dose level may resume up-dosing to the next dose level at the study site per protocol.
- Subjects who stopped study product and did not discontinue from the study may reinitiate dosing at the study site following approval from the medical monitor as described in [Section 4.2, Table 1](#), and [Table 2](#).

2.4.3 Maintenance Period

The duration of maintenance treatment for individual subjects will be extended as needed to accommodate any delays due to the restrictions.

Subjects in the maintenance period of study treatment will continue daily dosing at their current dose level of study product until study site visits resume. Dose adjustments may be allowed ([Section 4.1, Table 1](#)).

When study site visits resume, study treatment will continue or resume under medical supervision at the study site as follows:

- Subjects who continued daily dosing at 300 mg/day may continue their maintenance treatment regimen per protocol.
- Subjects who had dose reductions during the maintenance period will follow dose re-escalation procedures per protocol.
- Subjects who stopped study product and did not discontinue from the study may reinitiate dosing at the study site following approval from the medical monitor as described in [Section 4.2, Table 1](#), and [Table 2](#).

2.5 Remote Unscheduled Visits

Unscheduled visits may be performed remotely anytime to assess or follow up adverse events or at the request of the parent, caregiver, or investigator, or if additional study product is needed before the next scheduled remote study visit. The date and reason for the remote unscheduled visit must be recorded in the source documentation.

Noninterventional unscheduled visit procedures will be conducted as appropriate according to the protocol schedules of activities and the data recorded in the subject's source documents.

2.6 Early Discontinuation

Subjects who discontinue early from the study while restrictions are in place will have a remote early discontinuation visit approximately 14 days after their last dose of study product. Noninterventional early discontinuation procedures will be conducted according to the protocol schedule of activities and as described in [Section 2.4](#). Parents/caregivers will be encouraged to bring subjects back to the study site to complete all early discontinuation procedures when regular study site visits resume, unless consent is withdrawn.

Subjects with unresolved adverse events at early discontinuation while restrictions are in place or who had gastrointestinal (GI) adverse events of interest will have safety follow-up ([Section 2.8](#)).

The criteria for early discontinuation due to missed doses while restrictions are in place will be based on the guidance provided later in this appendix ([Figure 1, Table 1](#)). Depending on the reason and number of missed doses, certain subjects who miss doses and stop study product dosing when the restrictions are in place will not be discontinued early from the study. Such subjects may reinitiate dosing after study site visits resume. When regular study site visits resume, the regular protocol criteria for early discontinuation due to missed doses will apply.

2.7 Study Exit

Subjects who complete study treatment (initial dose escalation, up-dosing, and maintenance, which may be extended when restrictions are in place) will continue blinded study treatment and have remote study visits every 4 weeks until regular study site visits resume. Study exit will not occur until regular study site visits resume. Study exit procedures will be conducted in accordance with the study protocol.

2.8 Safety Follow-Up

In the event remote procedures are implemented, safety follow-up procedures will be conducted in accordance with the study protocol, except that subjects who discontinue due to GI adverse events will have remote study visits instead of study site visits when required, and no symptom-directed physical examinations will be performed.

Parents/caregivers of subjects who had GI adverse events of interest will be asked to complete the Pediatric Eosinophilic Esophagitis Symptom Scores version 2.0 (PEESS v2.0) per protocol.

3 TREATMENT COMPLIANCE

Accountability for the study product will be performed to document compliance with the dosing regimen. During remote study visits, parents/caregivers will be asked to return the study diary, all used study product packaging, and any unused capsules/sachets to the study site. If the return of these items is not feasible until the next study site visit, parents/caregivers will be asked to send photographs of the study diary (relevant pages), used study product packaging, and unused capsules/sachets to the study site for interim reconciliation with the study diary. Physical study product accountability and reconciliation with the study diaries will be performed after the materials are received at the study site. New study diaries will be dispensed as needed following completion of a remote study visit. Used study product packaging and unused capsules/sachets will not need to be stored at 2°C to 8°C.

Parents/caregivers will be asked to bring study diaries, used study product packaging, and unused capsules/sachets to the next study site visit if the return of these items to the study site is not feasible while restrictions are in place. Study site personnel must make reasonable efforts to obtain these items from parents/caregivers who do not return them at the next study site visit.

4 SAFETY CONSIDERATIONS

4.1 Dose Adjustment

The study product dose level may be continued or reduced, or the dose withheld per investigator judgment based on considerations including allergy symptoms, flare of atopic

[figure not shown]
disease unrelated to study product, intercurrent illness, treatment period (up-dosing vs maintenance), and access to local medical services.

The decision to reduce a dose level when a study site visit is not possible requires discussion and approval from the medical monitor and should occur as soon as possible to ensure timely dispensation of the study product. The reduced dose level will continue until study site visits resume and dose re-escalation can be attempted under medical supervision at the study site.

4.2 Missed Doses

Parents/caregivers will be instructed to contact the study site by the second day of consecutive missed doses if a second consecutive missed dose is anticipated. A remote unscheduled visit will be conducted to determine the reason for the missed doses (eg, adverse events, noncompliance) and to assess the safety of resuming the next dose at home. Access to local medical services should also be considered. The decision to resume study product dosing at a lower dose level after at least 2 consecutive missed doses should be made as soon as possible following discussion and approval from the medical monitor. If the consecutive missed doses were due to allergic adverse events and the dose level is assessed as not tolerated, dosing at the same dose level should not resume until regular study site visits resume.

Procedures for missed consecutive doses of study product when study site visits cannot be conducted are described in [Figure 1](#) and [Table 1](#). Subjects who stop study product dosing and do not discontinue early from the study may reinitiate dosing under medical supervision at the study site after study site visits resume and following discussion and approval from the medical monitor as described in [Table 2](#). Until study site visits resume, unscheduled visits should be performed monthly to review adverse events and concomitant medications (at minimum).

Figure 1: Procedures for Missed Consecutive Doses of Study Product

The guidance for 1 missed dose or 2 missed consecutive doses assumes that the current dose level is assessed as tolerated if dosing is continued at the current dose level.

[1] At investigator discretion, the subject may be observed by video call during and after administration of the next dose of study product at home.

Table 1: Description of Actions for Missed Consecutive Doses of Study Product

Missed Doses	Action
1 dose for any reason [1]	Resume next dose at current dose level at home.
2 consecutive doses for any reason [1]	Complete a remote study visit by the second consecutive day a dose is anticipated to be missed. If dosing can resume the next day, resume next dose at current dose level at home at investigator discretion. If a third consecutive dose is likely to be missed, follow action for missing 3 consecutive doses for any reason.
3-4 consecutive doses for any reason	Complete a remote study visit by the second consecutive day a dose is anticipated to be missed. Consider resuming next dose at ≤ 50% of previous dose (rounded down to the nearest feasible whole dose) at home if considered safe and following discussion and approval from the medical monitor. At investigator discretion, the subject may be observed by video call during and after administration of the next dose of study product. If continued dosing is assessed as not safe or dosing cannot resume by the day after 4 consecutive missed doses, stop study product dosing and inform the medical monitor. Subject may remain in the study and reinitiate dosing when study site visits can resume and following discussion and approval from the medical monitor.

Missed Doses	Action
≥ 3 consecutive doses on 3 occasions due to noncompliance	Stop study product dosing and discontinue the subject early from the study.
5-7 consecutive doses due to noncompliance ≥ 5 consecutive doses due to reasons other than noncompliance (eg, adverse event, epidemic- or pandemic-related reasons)	Stop study product dosing and inform the medical monitor. Subject may remain in the study and reinitiate dosing when study site visits can resume and following discussion and approval from the medical monitor.
> 7 consecutive doses due to noncompliance	Stop study product dosing and discontinue the subject early from the study.

[1] The guidance assumes that the current dose level is assessed as tolerated if dosing is continued at the current dose level.

Table 2: Reinitiation of Study Treatment After Stopping Study Product

Number of Days Since Last Dose	Action [1]
≤ 14 days during any period	Resume dosing per protocol [2]
> 14 days during initial dose escalation	Reinitiate dosing from initial dose escalation day 1
15-30 days during up-dosing or maintenance	Reinitiate up-dosing at 1 mg
> 30 days during up-dosing or maintenance	Reinitiate dosing from initial dose escalation day 1

Resumption of dosing under medical supervision at the study site requires discussion and approval from the medical monitor.

[1] Additional procedures for subjects who stopped study product dosing for > 14 days are as follows:

- Confirm that the subject has no clinically significant change in health status (eg, severe or uncontrolled asthma, eosinophilic esophagitis or other eosinophilic gastrointestinal disease, chronic or recurrent gastrointestinal adverse events of unknown etiology) or any other health condition that would preclude participation in the study, in the opinion of the investigator.
- Obtain medical monitor approval before reinitiating dosing.
- When up-dosing is reinitiated, dose escalation may resume per protocol.

[2] Subjects who completed day 1 but not day 2 of initial dose escalation at the time remote procedures were implemented will repeat day 1 of initial dose escalation.

5 STATISTICAL METHODS

Changes to the statistical methods and data presentations for reporting the study due to any restrictions will be detailed in the statistical analysis plan.

Limits to the prespecified maximum duration of up-dosing and maintenance periods for subjects to meet the criteria of responders at the exit food challenge will continue to apply, with the exception of any duration of time affected by the restrictions as defined by the first and last consecutively affected study visits. For instances of multiple distinct durations of

restriction, the maximum duration of the up-dosing and maintenance periods will be extended by the cumulative sum of these distinct durations of affected study visits.

Subjects who discontinue early from the study for any reason before completing their scheduled exit food challenge, including due to the restrictions, will be counted as nonresponders in an intent-to-treat analysis, and may also be excluded from an alternative sensitivity analysis of the primary and prespecified secondary endpoints as appropriate.

Additional subjects may need to be enrolled to accommodate a potential increase in dropouts, a substantial extension of the up-dosing period, or a substantial delay in completion of exit food challenges. In the event a greater than anticipated number of subjects discontinue early from the study due to the restrictions, the study sample size may be increased by up to 20% without protocol amendment. The sponsor may perform one or more blinded sample size reassessments, potentially in consultation with an external unblinded data and safety monitoring committee, to address any safety concerns associated with an increase in the study sample size.

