3 INVESTIGATIONAL PLAN

3.1 Overall Study Design and Plan: Description

This is a phase 3, international, randomized, double-blind, placebo-controlled study of the efficacy and safety of AR101 in peanut-allergic children aged 1 to < 4 years. The study will be conducted at approximately 25 study sites in North America and Europe.

Eligible subjects who develop age-appropriate dose-limiting allergy symptoms after consuming single doses of peanut protein > 3 mg to \leq 300 mg in a screening DBPCFC will be randomly assigned 2:1 to blinded treatment with AR101 or placebo. Randomization will be stratified by geographic region (North America, Europe).

Subjects will begin initial dose escalation under medical supervision at the study site on day 1 with a stepwise dose escalation of study product (up to 4 single doses of 0.5, 1, 1.5, and 3 mg) administered at 20- to 30-minute intervals as tolerated. Subjects who tolerate the 3 mg dose on day 1 will return on day 2 for a single 1 mg dose. Subjects who tolerate the 1 mg dose with no more than mild allergy symptoms that are not dose-limiting will begin the up-dosing period. Subjects who do not tolerate any dose on day 1 or day 2 will discontinue early from the study.

The up-dosing period will be approximately 6 months (maximum 40 weeks), with dose escalation approximately every 2 weeks. Daily doses of study product during up-dosing will be 1, 3, 6, 12, 20, 40, 80, 120, 160, 200, 240, and 300 mg/day. The first dose of study product at each new dose level will be administered under medical supervision at the study site; the remaining doses at each dose level will be administered daily at home as tolerated. Dose adjustments may be allowed. Subjects who tolerate the 300 mg/day dose for 2 weeks within 40 weeks will begin the maintenance period. Subjects unable to tolerate the 300 mg/day dose for 2 weeks within 40 weeks of up-dosing will discontinue early from the study.

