5.2.3.2 Up-Dosing Procedures

Up-dosing procedures are listed in the schedule of activities in [Appendix 5](#).

Up-dosing study site visits are every 2 weeks for approximately 6 months (minimum 24 weeks if up-dosing proceeds without holding or reducing a dose level; maximum 40 weeks).

Up-dosing will begin when subjects begin daily dosing with study product at 1 mg/day at home for 2 weeks. Subjects who tolerate 1 mg/day for 2 weeks will return to the study site to receive a 3 mg dose. Subjects who tolerate the 3 mg dose at the study site will receive study product to continue daily dosing at home with 3 mg/day for a total of 2 weeks. AR101 dose escalations will continue in this manner up to 300 mg/day as shown in [Table 3](#). Dose adjustments may be allowed ([Section 8.6.3](#), [Section 8.6.4](#)).

Subjects able to tolerate 300 mg/day for 2 weeks within 40 weeks will begin maintenance treatment ([Section 5.2.3.3](#)). Subjects will discontinue early from the study if unable to tolerate 300 mg/day for 2 weeks within 40 weeks, or if the dose level cannot be escalated after 3 consecutive failed attempts (with at least 2 weeks between each escalation attempt) ([Section 5.3](#)).

Additional procedures will be performed at the 80 mg and 300 mg up-dosing visits ([Appendix 5](#)).

Table 3: Up-Dosing Dose-Escalation Schedule (3-300 mg)

Dose Number	Study Product Dose (mg)	Interval (weeks)	Increase From Previous Repeated Dose
1	1	2	Not applicable
2	3	2	200%
3	6	2	100%
4	12	2	100%
5	20	2	67%
6	40	2	100%
7	80	2	100%
8	120	2	50%
9	160	2	33%
10	200	2	25%
11	240	2	20%
12	300	2	25%

Up-dosing begins with the first 1 mg/day dose of study product at home.

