5.2.3.3 Maintenance Procedures

The maintenance procedures are listed in [Appendix 5](#). The first maintenance visit will occur after 300 mg/day is tolerated for 2 weeks during up-dosing. Maintenance visits will occur every 4 weeks for an overall total of approximately 12 months of treatment. The duration of maintenance treatment may vary from a minimum of 12 weeks to a maximum of 24 weeks depending on the up-dosing interval (24-40 weeks). Dose adjustments may be allowed ([Section 8.6.3](#), [Section 8.6.4](#)).

After the end of maintenance, an exit DBPCFC will be performed ([Section 9.2](#), [Appendix 1](#), [Appendix 5](#)). The 300 mg daily dose of study product must be tolerated for at least 2 consecutive weeks before having the DBPCFC.

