2.3 Duration of Study

The total duration of the study and duration of study treatment for individual subjects will be extended as needed to allow subjects to complete study treatment following delays due to the restrictions.

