2.4 General Study Visit Procedures

Study visits will be conducted remotely (eg, telephone or video call) for subjects, parents, and caregivers who cannot attend scheduled visits at the study site due to the restrictions. Remote study visits will occur at the same intervals specified in the protocol schedules of activities.

On the day of a remote study visit, subjects will take their dose of study product at home per their usual dosing schedule.

During remote study visits, noninterventional visit procedures will be conducted according to the protocol schedules of activities as applicable and recorded in the subject's source documents:

- Adverse events review
- Concomitant medications review and instruction
- Treatment compliance/accountability review
- Diet/food allergen exposure review
- Food allergy instruction
- Asthma evaluation for subjects with asthma

Procedures that will not be completed during remote study visits are as follows:

- Weight, height, and vital signs measurements
- Questionnaires to assess atopic disease
 - Test for Respiratory and Asthma Control in Kids (TRACK)
 - Eczema Area and Severity Index (EASI)
- Physical examinations
 - Skin prick tests
 - Blood sample collection
- Food challenges
 - Food challenges will be delayed until the restrictions are lifted and regular study site visits resume. Food challenges are to be completed within 3 months after

regular study site visits resume for subjects who meet the protocol criteria for having a food challenge.

After completion of a remote study visit, study product will be dispensed as needed for dosing at home. Study site staff should confirm that study product was received by the appropriate individual.

After each remote study visit, site staff will contact the parent/caregiver by telephone within 3 days. In addition to the standard telephone call queries, receipt of study product will be confirmed (if applicable). The telephone call is at investigator discretion when study product is not dispensed after a remote study visit and dosing is continued at the same dose level.

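### Appendix 3 exempts only restriction time from the duration limits on responder status, so on a cumulative clock some children restarted as directed would be scored nonresponders

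*Combined protocol and SAP*

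**What the plan says.** **Main protocol.** Section 5.2.3.2 gives the length of up-dosing as "minimum 24 weeks if up-dosing proceeds without holding or reducing a dose level; maximum 40 weeks". Section 3.1 adds: "Subjects unable to tolerate the 300 mg/day dose for 2 weeks within 40 weeks of up-dosing will discontinue early from the study". Section 5.2.3.3 sets maintenance at 12 to 24 weeks, depending on how long up-dosing took. Section 10.5.1 defines response by the challenge dose tolerated. It counts withdrawal of consent and early discontinuation as nonresponse, and names no duration criterion.

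**Appendix 3, conduct.** Section 2.3 says that study and treatment duration will be "extended as needed to allow subjects to complete study treatment following delays due to the restrictions". Section 2.4.2 says: "The duration of up-dosing for individual subjects will be extended to accommodate any delays due to the restrictions". Section 2.4.3 says the same in substance for maintenance. None of these has a cap. Table 2 in Section 4.2 directs "Reinitiate up-dosing at 1 mg" after 15 to 30 days off product in up-dosing or maintenance, and a return to initial dose escalation day 1 after more than 30 days. Section 4.2 places the restart at the site, after site visits resume. On the exit challenge, Section 2.4 says "Food challenges are to be completed within 3 months after" regular site visits resume, for children who meet the criteria for a challenge.

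**Appendix 3, scoring.** Section 5 says that the prespecified maximum durations for a subject to qualify as a responder still apply, apart from time affected by the restrictions. That time is bounded by the first and last consecutively affected visits. For several separate restrictions, "the maximum duration of the up-dosing and maintenance periods will be extended by the cumulative sum of these distinct durations of affected study visits".

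**The concern.** The conduct text and the scoring text work to different rules. Conduct is open-ended: a child who lost supply is restarted and treatment is lengthened to fit. Scoring lengthens the limit only by the restriction itself. The re-escalation that Table 2 requires takes place after site visits resume, so it lies outside the exempted interval.

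A child could therefore restart as directed, reach 300 mg/day, tolerate 600 or 1000 mg at exit and still fall outside the limit. There are two routes to a nonresponder score: directly through Section 5 of Appendix 3, or through the 40-week discontinuation rule and then Section 10.5.1. The loss would fall mainly on AR101, because few placebo children are expected to respond. The primary difference would shrink for a reason unrelated to the product.

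**Working it through.** **Inputs.** 12 dose levels of 2 weeks each (Table 3 of the protocol); 40-week up-dosing maximum (Section 5.2.3.2); restart rules (Appendix 3, Table 2); exemption from first to last affected visit (Appendix 3, Section 5); 88 and 44 children, response rates 55% and 15%, two-sided 0.05 (Section 10.3); margin 0.15 (Section 10.5.1).

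**The plan's own figures.** Up-dosing from 1 mg takes 12 × 2 = 24 weeks, as stated. North America power by the Farrington-Manning test is 85.0% by the normal approximation and 85.4% by exact enumeration, against a stated 85%. Europe (50% against 10%, margin 0) gives 99.9%, against a stated figure above 95%.

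**Timeline on a cumulative clock.** Let u be the weeks of up-dosing before the first affected visit and R the exempted restriction time. After a restart at 1 mg, the child stays within the limit only if

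u + R + 24 ≤ 40 + R, that is, u ≤ 16.

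| Weeks before first affected visit (u) | Up-dosing net of R (u + 24) | Over 40 weeks by |
|---|---|---|
| 10 | 34 | within limit |
| 16 | 40 | within limit, no slack |
| 18 | 42 | 2 |
| 24 (fastest entry to maintenance) | 48 | 8 |
| 40 (slowest entry to maintenance) | 64 | 24 |

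The figure of 24 weeks is a minimum. Any later hold or dose reduction adds to it.

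**Where u is measured.** It stops at the first affected visit, not at the day dosing stopped, because home dosing during the restriction is already inside R. Suppose restrictions begin at week 10, and the child doses at home to week 20, misses 20 days and restarts. Counted up-dosing is 10 + 24 = 34 weeks, which is within the limit.

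**Effect on power (assumed losses).** The documents give no count of affected children. Each AR101 responder lost is 1/88 = 1.1 points. Two lost gives 55.0 − 2.3 = 52.7%; four lost gives 55.0 − 4.5 = 50.5%. Exact power with placebo at 15% and margin 0.15:

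| AR101 responders lost of 88 | AR101 rate | Power, 88 and 44 | Power, 105 and 53 |
|---|---|---|---|
| 0 | 55.0% | 85.4% | 91.4% |
| 2 | 52.7% | 78.3% | 85.8% |
| 4 | 50.5% | 69.6% | 78.1% |

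The last column is the 20% enlargement allowed by Appendix 3, Section 5 (132 × 1.2 = 158, split 2:1), with the same rates. For Europe at 88 and 44, the same losses (50% falling to 47.7% or 45.5%) leave power above 99%.

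**The case against.** The strongest reply is that the clock may restart. Table 2 speaks of reinitiating up-dosing, its footnote lets escalation resume per protocol, and Table 3 of the protocol dates up-dosing from the first 1 mg home dose. On that reading a restarted child needs 24 of 40 weeks and nothing is exceeded. Section 5 also foresees a substantial extension of up-dosing, and does not say exactly when affected time ends. This stands as a possible reading, but no passage states it. The summing of restriction periods in Section 5 points to a running total, and Section 5 is the only text that addresses responder status under restrictions.

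A second reply is that Section 5 leaves restriction-related changes in method to the SAP. The document reviewed contains no separate SAP text, so I cannot say that the rule is missing there.

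Third, few children may be affected. Product can be shipped, visits held remotely and home dosing continued, all of which make gaps of 15 days or more less likely. That is fair, and it is why the size is left open.

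Three stronger readings are tempting and not supported:

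- **Every child who stops after week 16 is over the limit.** The week-10 example above shows otherwise. Children who kept dosing at home need no restart.
- **The 3-month challenge window itself breaks the 24-week maintenance maximum.** If fully used and counted as maintenance, it would give 25 to 37 weeks (12 + 13 to 24 + 13). But it is an upper limit for children who already meet the challenge criteria, and a prompt challenge adds nothing. Section 5.2.3.3 also places the challenge after maintenance has ended. This is only a point to clarify.
- **Affected children certainly cannot count as responders.** That follows only on the cumulative reading.

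**Conclusion.** The scoring rule in Appendix 3, Section 5 does not fit the restart table or the uncapped extensions in Sections 2.3, 2.4.2 and 2.4.3, and it brings in a duration criterion that Section 10.5.1 does not name. Read literally with a cumulative clock, it scores as nonresponders restarted children who had more than 16 weeks of up-dosing before the first affected visit, and those already in maintenance, by 8 to 24 weeks in the latter case if there is no further delay. Children who kept dosing at home are not affected. Nor are restarted children with 16 weeks or less before the first affected visit and no other delay.

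Any bias is toward zero, so it does not threaten the type I error. Its size is unknown. The fall in North America power to 78%-70% rests wholly on the assumed loss of 2 to 4 AR101 responders with no enlargement of the sample. Because the rule decides primary-endpoint classification and is cheap to settle, it should be fixed.

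**What to change.** In Appendix 3, Section 5 and the SAP, state for both arms and for scoring responder status only:

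1. The re-escalation time that Table 2 requires is excluded from the duration limits, together with the restriction time.
2. Waiting time for a challenge held within the 3-month window does not count as maintenance.

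Taking re-escalation time as the time to regain the level held at the stop, a child with u = 18 and no delays, who stopped at the level held at the first affected visit, would be counted at 18 + 24 − 18 = 24 weeks instead of 42.

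Write this before any subject is unblinded. Sections 3.3 and 5.4 unblind each child individually after exit, so a later decision could be taken with assignments known.

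Sections 5.2.3.2 (including the 40-week discontinuation rule) and 10.5.1, and Appendix 3 Sections 2.3, 2.4, 2.4.2, 2.4.3, Table 2 and Section 5, must be reconciled with one another. No restart, dosing or discontinuation rule is proposed here.

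The cost is one paragraph. The downside is small: a few responders will have had longer total treatment, and they can be listed.
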